5.1 Study Leadership Error! Bo	
CONFLICT OF INTEREST POLICY Error! Bo	
LITERATURE REFERENCES Error! Bo	okmark not defined.
PENDIX Error! Bo	okmark not defined.

Version 01.2 Protocol:201607761 Version 01.2

LIST OF ABBREVIATIONS

SUDEP	Sudden unexpected and unexplained death in patients with epilepsy
HCVR	Hypercapnic Ventilatory Response
VE	Minute Ventilation
ETCO2	End tidal carbon dioxide
VRTCO2	Ventilatory recruitment threshold for carbon dioxide
EMU	Epilepsy Monitoring Unit

STATEMENT OF COMPLIANCE

The trial will be carried out in accordance with Good Clinical Practice (GCP) as required by the following (use applicable regulations depending on study location and sponsor requirements; examples follow): • United States (US) Code of Federal Regulations (CFR) applicable to clinical studies (45 CFR Part 46, 21 CFR Part 50, 21 CFR Part 56, 21 CFR Part 312, and/or 21 CFR Part 812) • ICH E6 All key personnel (all individuals responsible for the design and conduct of this trial) have completed Human Subjects Protection Training.

I agree to ensure that all staff members involved in the conduct of this study are informed about their obligations in meeting the above commitments.

Principal Investigator: _	[name]	
	Print/Type Name	
Q	mfgrð	
Signed:		Date: 6/28/2017

Version 01.2 Protocol:201607761 06/28/2017

PROTOCOL SUMMARY

Title: Abnormal ventilatory response to carbon dioxide in epilepsy patients: a

potential biomarker for seizure induced respiratory depression &

modification by SSRI- a pilot study

Précis: Double blind randomized phase II clinical trial.

Patients with epilepsy either undergoing video EEG study or being planned for one, will be screened by HCVR test. Fourty subjects with a depressed response (slope <2.0 L/mim/mm Hg) will be randomized to either

fluoxetine or placebo (1:1)

Intervention will be for 6 weeks.

Subjects will be enrolled in two different locations, EMU or neurology clinic. A follow up HCVR testing will be done at one month.

Continuous VEEG, and comprehensive respiratory monitoring (chest & abdominal belts, oro-nasal pressure & thermistry, pulse oximeter and trancutanesous CO₂ monitor) will be collected.

Change in the HCVR before and after intervention in two groups will be compared to determine effect of the drug. Similarly, differenc in severity of peri-ictal respiratory abnormalities will be compared between two arms.

Objectives: Primary Objective:

To assess feasibility of successfully enrolling subjects

Secondary Obective:

To evaluate effect of fluoxetine on HCVR and peri-ictal respiratory

depression in drug resistant epilepsy patients.

Version 01.2 Protocol:201607761 Version 01.2

Endpoint Primary End point:

Study recruitment rate assessed every 3 months through the study

completion

Study retention rate assessed every 3 months through the study completion

Secondary End point:

Change in mood score using PHQ-9 score

Change in minute ventilation during HCVR testing

Change in slope of HCVR

Difference in duration of abnormal breathing in periocal period

Difference in oxygen saturation during periotal period

Difference in CO₂ level in periotal period

Exploratory End points: Change in VRTCO₂

Change in time to VRTCO₂

Change in time to end of HCVR testing

Population: Subjects age 18-75 years, both genders, drug resistant epilepsy with no

prior severe depression or other psychiatry co-morbidities but otherwise healthy, mostly living in State of Iowa will be screened for this study.

Phase: 2 Number of Sites 1

enrolling participants:

[figure not shown]
Description of Study Fluoxetine, given by mouth with a standard titration over 6 weeks.

Agent: 10 mg for 1 week, 20 mg for 1 week, 40 mg for 2 weeks, 20 mg for 1 week,

10 mg for 1 week then STOP

Study Duration: 2 years **Participant Duration:** 6 weeks

Version 01.2 Protocol:201607761 06/28/2017

Version 01.2 Protocol:201607761 06/28/2017

I KEY ROLES

[name]

Role: Principal investigator

Institution: The University of Iowa,

Address: [name]

[contact] Email: [contact]

[name] Role: Co-Investigator

Institution: The University of Iowa,

Address: [name]

[contact] Email: [contact]

[name] Role: Co-Investigator

Institution: The University of Iowa,

Address: [name]

[contact] Email: [contact]

[name] PhD

Role: Co-Investigator

Institution: The University of Iowa,

Address: [name]

[contact]

Email: [contact]

[name] [name] Role: Biostatistician

Institution: The University of Iowa,

Address: [name]

[contact] Email: [contact]

[name] PhD

Role: Independent Medical Examiner Institution: The University of Iowa,

Address: [name]

2 INTRODUCTION: BACKGROUND INFORMATION AND SCIENTIFIC RATIONALE

2.1 BACKGROUND INFORMATION

Sudden unexpected death in epilepsy patients (SUDEP) ranks second only to stroke among neurological diseases in years of potential life lost (YPLL). While the specific mechanisms of death in SUDEP are not well understood, per-ictal respiratory dysfunction likely plays an important role in many cases. Seizure related respiratory depression of variable severity is commonly observed, and on rare instances may be fatal. There is a gap in our knowledge regarding the mechanisms responsible for peri-ictal respiratory dysfunction. A better understanding of these mechanisms would open the door to interventions to decrease the risk of SUDEP.

Several lines of evidence support a critical role for the serotonergic system in central control of ventilation. Serotonin neurons in the raphe nuclei of the brainstem sense rising carbon dioxide and low pH, thereby stimulating breathing and arousal. These responses may serve as mechanisms that protect against asphyxia, particularly during sleep or the post-ictal state. In addition, data from animal and human studies also indicate that serotonin possesses independent anti-seizure properties. Finally, in mouse models of seizure-induced sudden death, pre-treatment with selective serotonin reuptake inhibitor (SSRI) agents prevents death following seizures. These observations led us to formulate our *central hypothesis*: that a subset of epilepsy patients has impaired central chemo-responsiveness as tested by the ventilatory response to inhalation of carbon dioxide (hypercapnic ventilatory response, HCVR), and this correlates with a greater degree of peri-ictal respiratory depression, thereby increasing the risk of terminal cardiorespiratory dysfunction and death. We further hypothesize that the administration of fluoxetine (an SSRI agent) to patients with a depressed HCVR will enhance CO₂ sensitivity, and reduce the severity of peri-ictal respiratory depression.

2.2 RATIONALE

Fluoxetine is an FDA approved drug commonly and safely used to treat depression, anxiety, obsessive compulsive disorder and eating disorders. Its toxicology has been well studied in animal and human. Fluoxetine has been used safely in human to modify HCVR in panic disorder population. However, it has been not studied yet in epilepsy population. We hypothesize that administration of fluoxetine (an SSRI agent) to patients with a depressed HCVR will enhance CO₂ sensitivity, and reduce the severity of perical respiratory depression.

2.3 POTENTIAL RISKS AND BENEFITS

Version 01.2 Protocol:201607761 Version 201.2

2.3.1 KNOWN POTENTIAL RISKS

Fluoxetine is a FDA approved antidepressant medicine which is used very frequently and safely. Some patients may experience some side effects that include: Nausea, diarrhea, anorexia, dry mouth, dyspepsia, insomnia, anxiety, nervousness, somnolence, tremor, decreased libido, abnormal dreams, headache, asthenia, flu like syndrome, fever, weight loss, Flatulence, constipation, rash, pruritus, abnormal vision etc. However, rare and serious side effects are also possible which include; worsening depression, increase suicidal thoughts or actions, mood swings, acting aggressive or violent, serotonin syndrome, severe allergic reaction- trouble breathing, swelling of face, tongue, eyes or mouth, rash, hives, abnormal bleeding if you are taking blood thinner coumadin warfarin (Coumadin®), a non-steroidal anti-inflammatory drugs (NSAIDs, like Ibuprofen or naproxen), or aspirin, increase in seizure frequency and possible irregular heart rhythm called Torsades de pointes due prolonged OT.

Fluoxetine is classified by FDA as category "C" for use in pregnancy which means there is a known risk of birth defect animal fetus but there are no adequate data and well-controlled studies in human. Stopping fluoxetine suddenly can cause serious symptoms including:

- Anxiety, irritability, high or low mood, feeling restless or changes in sleep habits
- Headache, sweating, nausea, dizziness
- Shaking, confusion etc

2.3.2 KNOWN POTENTIAL BENEFITS

Improvement in mood.

3 OBJECTIVES AND PURPOSE

Primary Object: To assess feasibility of successfully enrolling subjects

Secondary Obect: To evaluate effect of fluoxetine on HCVR and peri-ictal respiratory depression in drug resistant epilepsy patients.

4 STUDY DESIGN AND ENDPOINTS

4.1 DESCRIPTION OF THE STUDY DESIGN

Double blind placebo-controlled randomized prospective trial

Two enrolling locations: EMU and Neurology Clinic

1) To test effect of Fluoxetine on HCVR: Subjects will be screened in the EMU and neurology clinic. Subjects eligible are those with patients with epilepsy who have a reduced baseline HCVR slope (<2.0 L/min/mmHg). Subjects will be enrolled, and randomized to either fluoxetine or placebo (1:1) until 20 subjects complete the study. Investigational Drug Services (IDS), at the University of Iowa Hospitals and Clinics (UIHC), will be responsible for randomizing and dispensing the

Version 01.2 Protocol:201607761 Version 20.2 Version 01.2

drugs. Both fluoxetine and placebo will be encapsulated in identical casing to mask their identity. Both the subjects and the investigators will be blinded to the randomization process. A standard titration plan will consist of fluoxetine or placebo 10 mg per day for a week, then 20 mg per day for a week and then 40 mg per day for 2 weeks, upon discharge. Subjects will return after 4 weeks for follow up HCVR testing in the Clinical Research Unit at UIHC. For each subject, the magnitude of post-treatment HCVR in terms of HCVR slope, minute ventilation, VRTCO₂, time to VRTCO₂ and time to target ETCO₂ at the end of the study will be compared with their baseline HCVR. The medication adherence rate, safey concerns and change in mood scale will be assessed at follow up. Reported adverse effects will be collected for all subjects. Enrolment rate and study completion rates will also be assessed every 6 months.

• 2) To test effect of fluoxetine on peri-ictal respiratory depression: Subjects will be screened in neurlogy clinic from a group of previously diagnosed patients with epilepsy who are planned for VEEG study. Eligible subjects will undergo HCVR testing. Eligible subjects with a reduced baseline HCVR slope (<2.0 L/min/mmHg) will be enrolled and randomized to fluoxetine vs placebo (1:1) until a total of 20 subjects complete the study. Both the subjects and investigators will be blinded to the randomization process. A standard titration plan for fluoxetine & placebo will be as above, for 4 weeks prior to EMU admission. During EMU admission, the subjects will be monitored with VEEG, EKG, EMG, SpO₂, tcCO₂/ETCO₂, oral & nasal thermistor & pressure transducer to measure airway pressure, and RIP with abdominal & chest belts to measure change in circumference during respiration. Peri-ictal respiratory changes in the two groups will be compared to assess the effect of fluoxetine.

4.2.1 PRIMARY ENDPOINT

Study recruitment rate assessed every 3 months Study completion rate assessed every 3 months

4.2.2 SECONDARY ENDPOINTS

Change in mood score using PHQ-9 score Change in minute ventilation during HCVR testing Change in slope of HCVR Difference in duration of abnormal breathing in periictal period Difference in oxygen saturation during periictal period Difference in CO₂ level in periictal period

4.2.3 EXPLORATORY ENDPOINTS

Change in VRTCO₂ Change in time to VRTCO₂ Change in time to end of HCVR testing

Version 01.2 Protocol:201607761 Version 20.2 Version 01.2

We will compare all the secondary outcome and exploratory measures using generalized linear models (GLMs), specifying an identity link for normally distributed data and the log link for right-skewed data.

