10.4 DESCRIPTION OF STATISTICAL METHODS

10.4.1 GENERAL APPROACH

Categorical data descriptive statistics will be presented as percentages, while continuous data descriptive statistics will be presented with the mean and standard deviation. Due to our goal of establishing estimates of centrality and spread for various measures to be used in future studies, no inferential tests will take place in this study.

Version 01.2 Protocol:201607761 Version 20.2 Version 01.2

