10.4.3 ANALYSIS OF THE SECONDARY ENDPOINT(S)

Observations with missing data are dropped from those analyses involving data variable.

Change in mood score using PHQ-9 score

This will be analyzed as the difference in PHQ-9 scores from baseline to final measurement between drug and placebo. The mean and standard deviation estimates of the differences will be provided.

Change in minute ventilation during HCVR testing:

This will be analyzed as the difference in minute ventilation during HCVR testing from baseline to final measurement between drug and placebo. The mean and standard deviation estimates of the differences will be provided.

Change in slope of HCVR

This will be analyzed as the difference in slope of HCVR between drug and placebo. Using a linear mixed model, we will include a predictor that is the interaction between HCVR slope and the treatment group. The mean and standard deviation estimates of the differences will be provided.

Difference in duration of abnormal breathing during periotal period:

Mean duration of abnormal breathing during perictal periods between drug and placebo will be compared. The mean and standard deviation estimates of the differences will be provided.

Difference in oxygen saturation during periotal period

Mean drop in oxygen saturation during perictal period between drug and placebo will be compared. The mean and standard deviation estimates of the differences will be provided.

Difference in CO₂ level in periotal period

Mean change in CO₂ level in periocal period compared to pre seizure baseline will be compared between drug and placebo. The mean and standard deviation estimates of the differences will be provided.

All the secondary outcome measures will be estimated using generalized linear mixed models (GLMMs), specifying an identity link for normally distributed data and the log link for right-skewed data.

Since we are interested in obtaining estimates for future studies, we will not run non-parametric analyses, which only provide p-values.

Version 01.2 Protocol:201607761 Version 20.2 Version 01.2

Assessment of adverse events

All the adverse events will be recorded. Frequency of each adverse events will be compared between the two groups and tested using one tail t-test with type I error at 0.025

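### Sections 4.2.3 (GLM) and 10.4.3 (GLMM) name different models for the same secondary outcomes, and neither states the unit of analysis or the random effects

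*Combined protocol and SAP*

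**What the plan says.** Section 4.2.2 lists six secondary endpoints: changes in PHQ-9, minute ventilation and HCVR slope, and three peri-ictal measures (duration of abnormal breathing, oxygen saturation, CO₂).

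Two current sentences assign a model to them:

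- Section 4.2.3: "We will compare all the secondary outcome and exploratory measures using generalized linear models (GLMs", with an identity or log link according to the distribution.
- Section 10.4.3: "All the secondary outcome measures will be estimated using generalized linear mixed models (GLMMs", with the same two links.

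Within 10.4.3, HCVR slope also has its own sentence: "Using a linear mixed model, we will include a predictor that is the interaction between HCVR slope and the treatment group". PHQ-9 and minute ventilation are described as differences from baseline to the final measurement. The peri-ictal endpoints are described as means, for example "Mean duration of abnormal breathing during perictal periods between drug and placebo will be compared" and "Mean drop in oxygen saturation during perictal period between drug and placebo will be compared". For each endpoint, "The mean and standard deviation estimates of the differences will be provided".

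Section 10.4.11 covers the exploratory HCVR measures and names no model, so section 4.2.3 is their only model statement. Section 10.4.1 adds that "no inferential tests will take place in this study".

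**The concern.** An analyst cannot follow both sentences. For most endpoints the choice between a GLM and a mixed model turns on what one record is, and the plan never says.

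The gap matters most for the peri-ictal measures. They come from continuous monitoring during an EMU admission, when one participant may have several seizures. A GLM on seizure-level records would ignore the correlation between seizures in the same person. It would also give no separate estimate of between-participant and within-participant variance. Section 10.1 says the pilot exists to supply estimates for future studies, and those two components are what a later trial would need in order to choose its number of participants.

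Following 10.4.3 throughout does not settle the matter. Its random effects are unstated, and for an endpoint reduced to one change score per participant a mixed model has nothing to separate.

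**Working it through.** The plan gives no figure to reproduce. Section 10.5 states that there is no formal sample size calculation, and no alpha or power is given for these endpoints.

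**Inputs from the documents.** Section 4.1, part 2: 20 completers randomized 1:1 for the peri-ictal comparison, so about 10 per arm.

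**Assumed inputs.** The documents give neither the number of seizures per participant (m) nor the within-participant correlation (ICC). The ranges used are m = 1 to 5 and ICC = 0.1 to 0.7.

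**Step 1: standard error if each seizure is a separate GLM record.** Design effect DE = 1 + (m − 1) × ICC. The standard error is understated by a factor √DE. Coverage of a nominal 95% interval is 2Φ(1.96/√DE) − 1. For m = 3 and ICC = 0.5: DE = 1 + 2 × 0.5 = 2.0, √2.0 = 1.41, and coverage = 2Φ(1.386) − 1 = 83.4%.

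**Step 2: effect on the pooled SD.** With k = 10 participants in an arm and N = k × m records, the ratio of pooled seizure-level SD to true total SD is about √[(N − DE)/(N − 1)]. For m = 3 and ICC = 0.5: √(28/29) = 0.983.

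| m | ICC | DE | SE understated by | Coverage | Pooled SD / true total SD |
|---|---|---|---|---|---|
| 1 | any | 1.0 | 1.00 | 95.0% | 1.000 |
| 2 | 0.3 | 1.3 | 1.14 | 91.4% | 0.992 |
| 3 | 0.1 | 1.2 | 1.10 | 92.6% | 0.997 |
| 3 | 0.5 | 2.0 | 1.41 | 83.4% | 0.983 |
| 3 | 0.7 | 2.4 | 1.55 | 79.4% | 0.976 |
| 5 | 0.1 | 1.4 | 1.18 | 90.2% | 0.996 |
| 5 | 0.5 | 3.0 | 1.73 | 74.2% | 0.979 |
| 5 | 0.7 | 3.8 | 1.95 | 68.5% | 0.971 |

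**Step 3: check by simulation** (10 participants per arm, 20,000 runs, ICC = 0.5). Seizure-level records gave coverage of 82.7% at m = 3 and 73.2% at m = 5. One mean per participant gave 95.0% and 94.7%. A random-intercept model was not simulated.

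**Step 4: what pooling hides from a future trial.** Take total variance as 1. The variance of a participant mean is ICC + (1 − ICC)/m. At ICC = 0.5 this is 0.5 + 0.5/3 = 0.67 for m = 3, and 0.5 + 0.5/5 = 0.60 for m = 5. A later trial that analyses participant means but is sized on the pooled total SD would overstate its sample size by 1/0.67 = 1.5 times, or 1/0.60 = 1.67 times.

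**Step 5: the mixed model on one change score.** With a single value per participant and an identity link, dᵢ = μ + treatment effect + bᵢ + eᵢ. Only the sum Var(bᵢ) + Var(eᵢ) can be estimated, so the random intercept cannot be separated from the residual. If baseline and follow-up values are both entered as records, it can be. Section 10.4.3 does not say which layout is meant.

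**The case against.** A reader might infer that section 4.2.3 commits the trial to treating several seizures from one person as independent, and so to error bars that are too narrow. The documents do not support that. No section makes the seizure the record, and 10.4.3 describes the peri-ictal endpoints as means. A GLM on one mean per participant fits that wording and is valid. The plural in the duration sentence allows for several seizures but gives no count.

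The plan also promises means and SDs and names no standard error or confidence interval for these endpoints. The coverage figures therefore apply only to intervals that someone might add, and the promised SD is almost unaffected. The statistical section already specifies mixed models, the primary objective is feasibility, and at most three of six secondary endpoints are exposed. The identifiability point is conditional too, because 10.4.3 does not state that a single change score is the record.

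All of this stands, and it limits the size of the point. It does not remove the contradiction: both model sentences are current, neither takes precedence, and the unit of analysis and random effects are missing from both. Nor does an unbiased total SD supply the variance components.

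It is also fair to say that baseline adjustment goes beyond what is strictly needed to reconcile the two sections. It uses values already collected and should be added openly, with the planned change summaries kept.

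**Conclusion.** The contradiction is established from the text: two model classes for the same six secondary outcomes, with unit of analysis and random effects unstated.

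The numerical consequence is conditional. It requires that the GLM sentence prevails, that seizures are entered as separate records, that participants have more than one seizure, and that the within-participant correlation is positive. Over the assumed ranges with 3 to 5 seizures, standard errors would be understated by a factor of 1.10 to 1.95; with one seizure or one mean per participant there is no understatement. Only the three peri-ictal endpoints are exposed, and only through model-based standard errors or intervals and the unseparated variance components. The pooled total SD stays within about 3% of its true value.

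The documents do not show that the planned error bars are too narrow. This should be corrected before analysis, as a matter of specification.

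**What to change.** Make sections 4.2.3 and 10.4.3 agree, and specify the model by endpoint type:

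- **Peri-ictal endpoints.** Choose one: a GLM on one mean per participant, or seizure-level records with a participant random intercept, reporting between- and within-participant variance. In either case give the number of participants and seizures per arm.
- **PHQ-9, minute ventilation and the exploratory HCVR measures.** Use a GLM on the follow-up value with the baseline value as covariate. Keep the planned mean and SD of change as descriptive output. Name this model in 10.4.11 as well.
- **HCVR slope.** Either keep the linear mixed model of 10.4.3 and state its random effects, or explicitly replace it with the same baseline-adjusted model. It should not be overridden silently by a general sentence.

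The cost is protocol and SAP wording. No extra participants, visits or measurements are needed.

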5 STUDY ENROLLMENT AND WITHDRAWAL

5.1 PARTICIPANT INCLUSION CRITERIA

- 1. Adult patients aged 18 or older
- 2. Patients with epilepsy,
- 3. Native English speaker or adequate fluency in English to provide informed consent.
- 4. Female patients of child-bearing potential must be using two acceptable method of contraception, or willing to refrain from sexual intercourse during the study.

